3.2 Discussion of Study Design

The study is designed to assess the safety, tolerability, efficacy, PK, and PD of ATI-450 in patients with CAPS.

Many patients with CAPS achieve complete or near complete disease remission with currently available anti-IL-1 therapies. Therefore, the study is designed to minimize patient's time off anti-IL-1 therapy due to potentially harmful long-term complications that can result from prolonged relapse of disease symptoms.

The study is open-label and there is no washout period for anti-IL-1 therapy; patients enrolled in the trial will begin treatment with study medication (Day 1) on the day of their next scheduled dose of anti-IL-1 therapy. At the end of the 12-week treatment period, ATI-450 administration will be discontinued, and patients will delay administration of anti-IL-1 therapy until 7 days (+4 days) after the last dose of ATI-450.

The 12-week treatment period was selected to allow sufficient time to explore the efficacy of ATI-450 in maintaining disease remission, and to adequately rule out the potential for prolonged disease remission caused by the last dose of anti-IL-1 therapy. Due to its long $t_{1/2}$, this is particularly relevant in instances when canakinumab is used.

3.3 End of Study

A patient is considered to have completed the study if he/she has completed all study visits. The end of the study is defined as the date of the last visit or date of last procedure of the last patient in the study.

4 STUDY POPULATION

Prospective approval of protocol deviations to recruitment and enrollment criteria, also known as protocol waivers or exemptions, is not permitted.

4.1 Inclusion Criteria

The following inclusion criteria must be met for a patient to be eligible for inclusion in the study:

- 1. Diagnosis of Familial Cold Autoinflammatory Syndrome, Muckle-Wells Syndrome, or Neonatal Onset Multisystem Inflammatory Disease. Prior agreement between the Investigator and Aclaris for study eligibility is required for patients who do not have a molecular diagnosis of NALP3 mutations available (either testing not performed, or testing performed but negative) upon study entry. For those patients who have not been molecularly tested for NALP3 mutations, molecular testing should be performed during the course of the study.
- 2. Patients with a PGA score of "minimal" or less and who are considered to have achieved that response as a result of successful anti-IL-1 therapy.
- 3. Continuous treatment with anti-IL-1 therapy for at least 6 months.
- 4. Able to understand and comply with study procedures and was able to provide informed consent.
- 5. Male or non-pregnant, non-nursing female patients at least 18 years of age, inclusive.
 - Female patients who are of childbearing potential must use 2 methods of highly effective contraception* one of which must be a physical barrier- for the duration of the study and for 30 days after the last dose
 - Male patients of childbearing potential with a female partner of childbearing potential must agree to use a condom plus another highly effective form of birth control for the duration of the study and for 90 days after the last dose
- 6. Female patients must have a negative serum pregnancy test at screening and a negative urine pregnancy test prior to dosing on Day 1.
- 7. Willing and capable of taking appropriate Covid-19 risk mitigation precautions (e.g. wearing a mask in public, adhering to social distancing, etc.) as required or recommended by local, state, or federal guidelines during participation in the study.

*Highly effective birth control is defined as those which result in a low failure rate (i.e., less than 1% per year) when used consistently and correctly such as implants, injectables, combined oral contraceptives, some intrauterine devices, heterosexual abstinence, or vasectomized.

4.2 Exclusion Criteria

A patient who meets any of the following exclusion criteria will not be eligible for inclusion in the study:

1. Participation in any clinical study with an investigative agent within 12 weeks prior to entry or within 5 half-lives of the investigational agent.

- 2. Being treated with another immuno-suppressive agent (i.e., in addition to an anti-IL-1 product) for CAPS syndrome (anti- IL1 therapy will have been used for at least 6 months and will be stopped at study entry).
- 3. Use of any of the following treatments within the indicated washout period prior to the baseline visit:
 - a. Systemic immunosuppressant or immunomodulatory therapy (e.g., etanercept, alefacept, infliximab, methotrexate) within 16 weeks prior to Visit 2 (excluding anti-IL-1 therapy for CAPS).
 - b. Janus Kinase (JAK) inhibitors (systemic and topical) within 4 weeks prior to Visit 2.
 - c. Systemic corticosteroids within 4 weeks prior to Visit 2. (Intranasal, inhaled, and topical ocular corticosteroids are allowed).
- 4. History of being immunocompromised, including a positive HIV test result at screening.
- 5. A positive Hepatitis B surface antigen (HBsAg) or Hepatitis C antibody test result is not allowed.
- 6. Live vaccination within 3 months prior to the start of the trial, or during the trial.
- 7. History of recurrent and/or evidence of active bacterial, fungal, or viral infections.
- 8. History or evidence of active or latent tuberculosis (TB).
- 9. Tests performed at a central laboratory at screening that meet any of the criteria below (out of range labs may be rechecked one time, after consultation with sponsor or designee, before patient is considered a screen failure):
 - White blood cell (WBC) count $< 3.0 \times 10^3$ cells/mm³
 - Absolute neutrophil count (ANC) <1.5×10³ cells/mm³
 - Lymphocyte count <0.5×10³ cells/mm³
 - Platelet count <100×10³ cells/mm³
 - Hemoglobin <10 g/dL
 - Aspartate aminotransferase (AST) or alanine aminotransferase (ALT) ≥1.5×upper limit of normal (ULN)
 - Total bilirubin level $\ge 2 \times ULN$ unless the patient has been diagnosed with Gilberts' disease and this is clearly documented
 - Estimated glomerular filtration rate (eGFR), <40 mL/min/1.73m² based on Modification of Diet and Renal Disease formula
- 10. Any clinically significant laboratory abnormality that would affect interpretation of study data or safety of the patient's participation in the study, per judgment of investigator.
- 11. Patient has clinically significant abnormal findings other than CAPS from physical examination conducted at screening visit (Visit 1) and at baseline visit (Visit 2) that may affect the interpretation of study data or the safety of the patient's participation in the study, per the judgment of the investigator.
- 12. Patient has a clinically important history of a medical disorder that would compromise patient safety or data quality, per the judgment of the investigator.

- 13. Blood pressure (BP) levels (in supine position after at least 5 minutes rest) <90 mmHg or >140 mmHG for systolic BP or <40 mmHG or >90 mmHg for diastolic blood pressure.
- 14. Patients with history of stroke.
- 15. Significant cardiac disease that would affect interpretation of study data or the safety of the patient's participation in the study, per the judgment of the investigator, including recent myocardial infarction or unstable angina, or heart failure with New York Heart Association Class III or IV symptoms.
- 16. Patients with the following screening or pre-dose ECG findings, specifically:
 - Evidence of atrial fibrillation, atrial flutter, complete right or left bundle branch block, Wolff-Parkinson-White Syndrome, or other significant rhythm disturbance
 - Evidence of acute ischemia
 - Screening or pre-dose baseline mean QTcF >450 msec for males or >470 msec for females (use of the ECG algorithm is acceptable for this purpose)
 - Personal or family history of congenital long QT syndrome or sudden death
 - Any other finding that is considered clinically significant
- 17. A confirmed diagnosis of Covid-19 at baseline or at any time during the study.

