- 9. Tests performed at a central laboratory at screening that meet any of the criteria below (out of range labs may be rechecked one time, after consultation with sponsor or designee, before patient is considered a screen failure):
 - White blood cell (WBC) count <3.0×10³ cells/mm³
 - Absolute neutrophil count (ANC) <1.5×10³ cells/mm³
 - Lymphocyte count <0.5×10³ cells/mm³
 - Platelet count <100×10³ cells/mm³
 - Hemoglobin <10 g/dL
 - Aspartate aminotransferase (AST) or alanine aminotransferase (ALT) ≥ 2×upper limit of normal (ULN)
 - Total bilirubin level >2×ULN, unless patient has been diagnosed with Gilberts' disease and this is clearly documented

- Estimated glomerular filtration rate Estimated glomerular filtration rate (eGFR), <40 mL/min/1.73m2 based on Modification of Diet and Renal Disease formula
- 10. Any clinically significant laboratory abnormality that would affect interpretation of study data or safety of the patient's participation in the study, per the judgment of the investigator.
- 11. Patient has clinically significant abnormal findings other than CAPS from physical examination that may affect the interpretation of study data or the safety of the patient's participation in the study, per the judgment of the investigator.
- 12. Patient has a clinically important history of a medical disorder that would compromise patient safety or data quality, per the judgement of the investigator.
- 13. Blood pressure (BP) levels (in supine position after at least 5 minutes rest): <90 mmHg or >140 mmHg for systolic BP or <40 mmHg or >90 mmHg for diastolic blood pressure.
- 14. Patients with history of stroke.
- 15. Significant cardiac disease that would affect interpretation of study data or the safety of the patient's participation in the study, per the judgment of the investigator, including recent myocardial infarction or unstable angina, or heart failure with New York Heart Association Class III or IV symptoms.
- 16. Patients with the following screening or pre-dose ECG findings, specifically:
 - Evidence of atrial fibrillation, atrial flutter, complete right or left bundle branch block, Wolff-Parkinson-White Syndrome, or other significant rhythm disturbance
 - Evidence of acute ischemia
 - Screening or pre-dose baseline mean QTcF >450 msec for males or >470 msec for females (use of the ECG algorithm is acceptable for this purpose)
 - Personal or family history of congenital long QT syndrome or sudden death

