4.3 Screen Failures

Screen failures are defined as patients who consent to participate in the clinical study but who do not meet 1 or more criterion required for participation and are not subsequently progressed to treatment in the study. A minimal set of screen failure information is required to ensure transparent reporting of screen failure patients, to meet the Consolidated Standards of Reporting Trials publishing requirements, and to respond to queries from regulatory authorities. Minimal information includes demography, screen failure details, eligibility criteria, and any SAE(s).

Individuals who are screen failures due to out of range laboratory values can be rescreened once. Rescreened individuals retain the same screening number as used for the initial screening.

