4.4 Premature Discontinuation

4.4.1 Premature Discontinuation of Investigational Product

Patients should discontinue ATI-450 if any of the following occurs:

- Serious infection
- Invasive fungal infection
- Malignancy (except for non-melanoma skin cancer)
- Hepatitis B virus reactivation

- Demyelinating disease
- Heart failure
- Lupus-like syndrome
- Hypersensitivity reaction
- Gastrointestinal perforation
- WBC count: $<1\times10^3/\mu$ L
- ANC: $<0.5 \times 10^3 / \mu L$
- Lymphocyte count: $<0.3\times10^3/\mu$ L
- Platelet count: $<50\times10^3/\mu$ L
- Hemoglobin: <6.5 g/dL
- AST or ALT:
 - o ≥5×ULN persisting for 2-weeks after study medication interruption or second occurrence of ≥5×ULN
 - \circ ≥3×ULN and total bilirubin ≥2×ULN or international normalized ratio [INR] >1.5
 - ≥3×ULN with appearance of fatigue, nausea, vomiting, right upper quadrant pain or tenderness, fever, rash, and/or eosinophilia (>5%)
- Serum creatinine: >2×ULN persisting for 2-weeks after study medication interruption or second occurrence of >2×ULN
- Confirmed, active infection with the severe acute respiratory syndrome coronavirus 2 (SARS-CoV-2 virus)
- The patient withdraws his/her consent to participate in the study
- The patient develops an illness that would interfere with his/her continued participation in the study
- The patient is noncompliant with study procedures or medication, in the opinion of the investigator
- The patient is confirmed to be pregnant
- The sponsor or regulatory agency requests withdrawal of the patient

- Severe AEs or SAEs
- Any other reason relating to the patient's safety

The investigator will make every effort to ensure that patients who prematurely discontinue ATI-450 complete the end of study assessments.

Patients who discontinue ATI-450 prematurely may be replaced at discretion of the sponsor.

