5.3.2.1 Potential Drug-induced Liver Injury

Hy's Law cases have the following 3 components:

- 1. The drug causes hepatocellular injury, generally shown by a higher incidence of \geq 3-fold elevations above the ULN of ALT or AST than the placebo
- 2. Among study patients showing such aminotransferase elevations, often with aminotransferases much greater than 3×ULN, one or more also shows elevation of serum total bilirubin to >2×ULN or INR >1.5, without initial findings of cholestasis (elevated ALP)
- 3. No other reason can be found to explain the combination of increased aminotransferase and total bilirubin, such as viral hepatitis A, B, or C; evidence for biliary obstruction; acute alcoholic hepatitis (recent drinking and AST >2×ALT are supportive); recent history of severe hypotension or congestive heart failure; other underlying viral disease; pre-existing or acute liver disease; or another drug (including non-prescription products such as herbal supplements) capable of causing the observed injury

During the study, the investigator will remain vigilant for increases in liver biochemistry. The investigator is responsible for determining whether a patient meets potential drug-induced liver injury criteria at any point during the study.

In the event that a patient shows laboratory results of:

- AST or ALT:
 - >5×ULN persisting for 2-weeks after study medication interruption or second occurrence of >5×ULN

- \circ >3×ULN and (total bilirubin >2×ULN or INR >1.5)
- >3×ULN with appearance of fatigue, nausea, vomiting, right upper quadrant pain or tenderness, fever, rash, and/or eosinophilia (>5%)

Please refer to Appendix 1 Possible Hy's Law Liver Chemistry Action and Follow-up Assessments Possible Hy's Law Liver Chemistry Action and Follow-up Assessments for further information.

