16 APPENDICES

16.1 Appendix 1 Possible Hy's Law Liver Chemistry Action and Follow-up Assessments

Suggested Actions and Fe	ollow-up Assessments					
Actions	Follow-Up Assessments					
 Immediately discontinue study medication. Report the event to the sponsor or designee within 24 hours. Complete a SAE data collection tool if the event also met the criteria for an SAE.² Perform liver chemistry follow-up assessments. Monitor the participant until liver chemistry test abnormalities resolve, stabilize, or return to baseline (see MONITORING). Do not restart/re-challenge participant with study treatment unless allowed per-protocol and sponsor approval is granted. If restart/re-challenge is either not allowed per-protocol or not granted, permanently discontinue study treatment. The participant may continue in the study for any protocol-specified follow-up assessments 	 Viral hepatitis serology³ Obtain INR and recheck with each liver chemistry assessment until the transaminase's values show downward trend Obtain blood sample for ATI-450 drug concentration⁴ Serum creatine phosphokinase (CPK) and lactate dehydrogenase (LDH) Fractionate bilirubin if total bilirubin ≥2xULN Obtain complete blood count with differential to assess eosinophilia Record the appearance or worsening of clinical symptoms of liver injury, or hypersensitivity, on the AE eCRF Record use of concomitant medications 					
MONITORING: If ALT ≥3xULN AND bilirubin ≥2xULN or INR >1.5:	(including acetaminophen, herbal remedies, and other over-the-counter medications) on the concomitant medications CRF					
 Repeat liver chemistry tests (ALT, AST, ALP, bilirubin) and perform liver event follow-up assessments within 24 hours. Monitor participant twice weekly until liver chemistry test abnormalities resolve, stabilize, or return to baseline. A specialist or hepatology consultation is recommended. If ALT ≥3xULN AND bilirubin <2xULN and INR ≤1.5: Repeat liver chemistry tests (include ALT, AST, ALP, bilirubin) and perform liver chemistry follow-up assessments within 24 to 72 hours. 	fALT ≥3xULN AND bilirubin ≥ 2xULN or NR >1.5: Anti-nuclear antibody, anti-smooth muscle antibody, Type 1 anti-liver kidney microsomal antibodies, and quantitative total immunoglobulin G (IgG) or gamma globulins. Serum acetaminophen adduct enzyme immunoassay(quantifies potential acetaminophen contribution to liver injury in participants with definite or likely acetaminophen use in the preceding week.					

Page 68 of 71

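### Exclusion criterion 9 carries two different AST/ALT limits, so a screening value from 1.5 to below 2×ULN is excluded by Section 4.2 but not by the synopsis

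*Combined protocol and SAP*

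**What the plan says.** The synopsis and Section 4.2 each list the exclusion criteria, and in each list meeting any one criterion makes the patient ineligible. Criterion 9 covers screening tests at the central laboratory and allows one recheck of an out-of-range result after consultation with the sponsor or its designee.

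- Synopsis, criterion 9: "Aspartate aminotransferase (AST) or alanine aminotransferase (ALT) ≥ 2×upper limit of normal (ULN", and for bilirubin "Total bilirubin level >2×ULN, unless patient has been diagnosed with" Gilbert's disease.
- Section 4.2, criterion 9: "Aspartate aminotransferase (AST) or alanine aminotransferase (ALT) ≥1.5×upper limit of normal (ULN", with total bilirubin excluded at or above 2×ULN, subject to the same Gilbert's exception.

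Section 4 adds: "Prospective approval of protocol deviations to recruitment and enrollment criteria, also known as protocol waivers or exemptions, is not permitted". Section 4.3 adds: "Individuals who are screen failures due to out of range laboratory values can be rescreened once".

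The on-treatment liver rules are stated in three further places. Section 4.4.1 has "≥3×ULN and total bilirubin ≥2×ULN or international normalized ratio [INR] >1.5", Section 5.3.2.1 has ">3×ULN and (total bilirubin >2×ULN or INR >1.5", and Appendix 1 has "If ALT ≥3xULN AND bilirubin ≥2xULN or INR >1.5".

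**The concern.** An eligibility rule has to give one answer for each patient. Over a range of AST/ALT values this one gives two, and the answer depends on which page the site works from.

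Three things are at stake.

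- **Who enters.** Safety and tolerability are the primary objective, and the primary endpoint in Section 2 includes mean change from baseline in laboratory values. Sites using different pages would enrol under different liver limits.
- **What counts as a deviation.** Section 11.2 gives enrolment against key eligibility criteria as an example of an important deviation, which triggers a discussion about withdrawing the patient. A patient at, say, 1.7×ULN enrolled under the synopsis could be classed that way under Section 4.2. A patient at the same value who is turned away under Section 4.2 has not met the synopsis limit.
- **Whether the recheck and rescreening apply.** Both depend on the result being out of range, and that also depends on the page.

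**Working it through.** The plan states no figure to reproduce. The sample size rests on feasibility, so no power calculation is involved. The check is a comparison of the two rules.

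**Step 1. Are the two lists meant to be the same?** Criterion 9 has eight items:

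| Item | Synopsis excludes | Section 4.2 excludes | Same? |
|---|---|---|---|
| WBC (×10³/mm³) | <3.0 | <3.0 | yes |
| ANC (×10³/mm³) | <1.5 | <1.5 | yes |
| Lymphocytes (×10³/mm³) | <0.5 | <0.5 | yes |
| Platelets (×10³/mm³) | <100 | <100 | yes |
| Hemoglobin (g/dL) | <10 | <10 | yes |
| AST or ALT (×ULN) | ≥2 | ≥1.5 | **no** |
| Total bilirubin (×ULN) | >2 | ≥2 | only at exactly 2 |
| eGFR (mL/min/1.73 m²) | <40 | <40 | yes |

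Six of the eight agree and only the two liver items differ, so this looks like a failure to keep two copies in step. The summary of changes for Version 2.0 mentions exclusion criterion 4 but not the AST/ALT limit, so it does not explain the difference.

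**Step 2. Where do the AST/ALT rules disagree?** Let x be the higher of AST and ALT, each as a multiple of its ULN. The synopsis excludes if x ≥ 2; Section 4.2 excludes if x ≥ 1.5.

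| x | Synopsis | Section 4.2 |
|---|---|---|
| x < 1.5 | not excluded | not excluded |
| 1.5 ≤ x < 2 | **not excluded** | **excluded** |
| x ≥ 2 | excluded | excluded |

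The lists disagree over the whole range from 1.5 (inclusive) to 2 (exclusive) ×ULN.

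**Step 3. Does anything else settle it?** No clause ranks one list above the other. The recheck does not help, because the repeat value meets the same two limits. Criterion 10, on laboratory abnormalities the investigator judges clinically significant, could still exclude such a patient, but it does not supply the missing numeric limit.

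**Step 4. Illustration of the distance to the on-treatment limits.** The fold rise needed is the on-treatment limit divided by the screening value. Each list admits values strictly below its limit, so from the top of the admitted range the rise is just over:

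| Section 4.4.1 transaminase level | Synopsis (up to 2) | Section 4.2 (up to 1.5) |
|---|---|---|
| 3×ULN | 3/2 = 1.5 | 3/1.5 = 2.0 |
| 5×ULN | 5/2 = 2.5 | 5/1.5 = 3.33 |

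Reaching these levels does not by itself meet a discontinuation rule. The 3×ULN rules also need raised bilirubin, raised INR or symptoms. The 5×ULN rule needs persistence for 2 weeks after interruption, or a second occurrence.

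**Step 5. The on-treatment wording (minor, no effect on eligibility).** Section 4.4.1 uses ≥ for the transaminase limits in all three liver rules and for the bilirubin limit; Section 5.3.2.1 uses >; Appendix 1 uses ≥ for its 3×ULN and 2×ULN limits. These differ only at exact limit values. Section 4.4.1 also leaves the bilirubin/INR alternative unbracketed, so read literally a raised INR could stand alone. Section 5.3.2.1 brackets it, and Appendix 1 note 2 writes out the ALT and INR pair.

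**The case against.** The strongest case on the other side accepts the conflict and disputes its weight.

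- **An exclusion list does not tell a site to enrol anyone.** This stands as a point of wording: within the band the synopsis does not exclude on this item, and other criteria may. The two lists still lead to different decisions on the same result.
- **A site can ask the sponsor, and a clarification is not a waiver.** Also correct. The ban on waivers does not create the conflict; it only prevents the sponsor from approving exceptions patient by patient. A site reading only one list would have no reason to ask.
- **The fold-rise figures are weak.** Criterion 9 applies at screening, which may be as early as Day -56, and chemistry is repeated on Day 1. Baseline is the last value on or before first dosing, so criterion 9 does not fix the baseline value. This stands: the figures are correct arithmetic from the screening limits, but only an illustration from the extremes.
- **The effect is small.** One bullet in a study of up to 10 patients, with liver chemistry measured at every on-site visit and no efficacy definition involved. The scale is as described, but in so small a study one patient is at least 1/10 = 10% of a full sample, and the item is a safety limit.
- **The sign and bracket differences are marginal.** Agreed. They matter only at exact values, a sign could be altered when text is read from a PDF, and Section 5.3.2.1 and Appendix 1 already show the intended INR grouping. They deserve less confidence than 1.5 against 2 and are editorial.

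**Conclusion.** The concern holds. It is an internal inconsistency in a safety eligibility limit and must be fixed. AST or ALT from 1.5 to below 2×ULN is excluded by Section 4.2 and not by the synopsis, with no rule to decide between them. The bilirubin disagreement is confined to exactly 2×ULN.

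This conclusion needs no statistical assumption, only that both lists are current Version 2.0 text and concern the same test, which they state. How many patients would be affected is unknown: the documents give no distribution of screening transaminases.

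**What to change.** Reconcile criterion 9 between the synopsis and Section 4.2 so that the AST/ALT limit and the bilirubin limit, including its inequality sign, read identically. The sponsor decides the values; this review takes no position on them. If any patient has already been screened with AST or ALT from 1.5 to below 2×ULN, record which list was applied.

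In the same edit, align the inequality signs and the bracketing of the bilirubin/INR condition across Sections 4.4.1 and 5.3.2.1 and Appendix 1.

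The cost is protocol wording, processed as an amendment under Section 12. No visit, sample or analysis changes.
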